## 2 TRIAL OBJECTIVES AND OUTCOMES

**Table 1: Primary Objectives and Outcome Measures**

Primary Objective:	Outcome Measure:	Time point of outcome measured
To compare the efficacy of DAAs in HCV positive, active PWIDs, administered via DOT, fortnightly pick-up or fortnightly pick-up with a psychological adherence intervention.	SVR 12 rates of participants in the DOT, fortnightly pick-up or fortnightly pick-up with a psychological adherence intervention group	12 weeks post treatment completion

**Table 2: Secondary Objectives and Outcome Measures**

Secondary Objective:	Outcome Measure:	Timepoint of outcome measured
To demonstrate that the achieved SVR rates in HCV PWID participants with DAA treatment are similar to RCT results and therefore a cost-effective treatment	Adherence of daily directly observed therapy group from daily logs	Daily log completed daily, adherence calculated at end of treatment
	Adherence measured by counting tablets returned after each 2 week treatment period (fortnightly pickup groups)	Calculated at end of treatment
	Adherence of participants infected with genotype 3 and treated with Sovaldi measured using MEMS® cap.	Calculated at end of treatment
To assess reinfection rates in active PWIDs treated with oral DAA regimes	Hepatitis C viral load from PCR	Annually at clinic visits
To assess resistance profiles in those who do not achieve SVR.	Profiles of the HCV viral resistance proteins, NS5a and NS3	Blood collected at baseline, end of treatment and SVR 12
To assess the types of illicit drugs taken by trial participants and identify any interaction with the DAAs.	Drug misuse history	Baseline, end of treatment (genotype 1 infection = week12, genotype 3 infection= week8)
	Urine toxicology	Once during treatment

### 3 TRIAL DESIGN

#### 3.1 TRIAL DESCRIPTION

This is a randomised, un-blinded trial which will be conducted in the needle exchange services and pharmacies across Tayside, designed to evaluate the efficacy and feasibility of DAA therapy, in HCV positive, genotype 1 and 3, active PWIDs, administered via three different routes:

1. DOT,
2. Fortnightly pick-up
3. Fortnightly pick-up with psychological intervention.

Participants included in the trial will have a reactive Dry Blood Spot (DBS) test to confirm HCV infection, PCR to confirm active infection and will currently be using illicit drugs, as confirmed by the participant. Drug screening (by urine sample) will not be tested at that time.

Participants will be stratified by the genotype of their HCV infection; genotype 1 vs genotype 3 and randomised to one of three groups; DOT, fortnightly pick-up, or fortnightly pick-up with psychological adherence intervention.

All PWID are encouraged to have a DBS test annually as part of clinical practice in Tayside. Upon receipt of a reactive DBS test, potential participants will be briefed about the trial by the specialist nurse or other trained member of staff and given a participant information sheet (PIS) informing them of what is involved. Willing individuals will provide written informed consent and will then have safety bloods drawn to determine eligibility to proceed. A full list of inclusion/exclusion criteria is detailed in section 4.

Participants in all three arms of the trial will attend a baseline visit, a randomisation visit either one (genotype 3) or two (genotype 1) visits during treatment, an end of treatment visit and an SVR visit, as detailed in Appendix 2.

All participants will be given incentives to continue with their treatment in the trial. These will consist of protein drinks and will be given at each study visit.

#### *Psychological intervention*

Participants randomised to fortnightly pick-up with psychological intervention will have an interview with the study nurse, prior to beginning their treatment, which will cover the educational intervention designed to aid their compliance with the drug regimen. The intervention will be based on the Information-Motivation-Behavioural (IMB) Skills Model of Adherence which was originally developed to explain adherence behaviour in HIV. Recent research suggests this model may have applicability in understanding the facilitator and barriers to adherence in HCV patients. The model suggests that provision of medication information, enhancing personal and social motivation and developing behavioural skills that are key determinants of adherence and may improve adherence in this group. The intervention will involve a structured interview in which the trial nurse and participant will develop an action plan that includes personalised information, sources of motivation for adherence and a treatment routine configured to be compatible with the participant's lifestyle. Anticipating barriers to adherence and problem-solving will be included in the treatment routine. The intervention will take place at the randomisation visit and last approximately one hour. During the intervention, participants will be guided by their trial nurse in the completion of a personalised booklet, "Hepatitis C and Me". The booklet contains general and personalised information on Hepatitis C, exercises designed to explore and enhance personal and social motivation for treatment adherence and a behavioural action plan (the skills element of the IMB model). The booklet

uses the principles of node-link mapping to structure the intervention. Node link mapping use a set of visual tools to structure and guide therapeutic conversation and has been shown to enhance memory and compliance with treatment in substance misusers (e.g 13,14). Participants in the other two arms of the trial, who are not receiving the psychological intervention, will be given the current NHS Tayside hepatitis information booklet ("Living with Hepatitis C") which provides generalised information about HCV without personalised information or specific strategies to enhance motivation and behavioural skills.

*Reinfection follow up.*

Trial participants will be invited to also consent for access to information from their annual clinic visits and HCV testing at any other contact with clinical services for up to 5 years, to detect re-infection.

*Illicit drug monitoring*

Illicit drug use will be recorded at baseline and at end of treatment (week 8 for genotype 3, week 12 for genotype 1). One sample of urine for toxicology will be taken during treatment. Those participants who fail to achieve SVR will be compared to successful participants for any correlation with particular substance use. For any candidate substance associated with failure to achieve SVR not explained by lack of adherence, biological samples will be analysed for biological mechanisms.

*Adherence monitoring*

Adherence of those participants randomised to DOT will be documented on a daily log. Those randomised to fortnightly collection of medication will receive Zepatier tablets in blister packaging. They will return their packets of medication every two weeks and any remaining tablets will be counted. Participants infected with HCV genotype 3 will additionally receive bottles containing Sovaldi tablets. These bottles will be fitted with adherence aid caps that record time and date of each cap opening.

### **3.2 TRIAL FLOWCHART**

Please refer to Appendix 1 (section 17.1)

### **3.3 TRIAL MATRIX**

Please refer to Appendix 2 (section 17.2).

## **4 TRIAL POPULATION**

### **4.1 NUMBER OF PARTICIPANTS**

This trial aims to treat 135 active PWID with active HCV infection in Tayside over a two year period. Due to the nature of this trial, trial dropouts are a trial endpoint and will not be replaced.

#### **4.2 INCLUSION CRITERIA**

- Male or Female. (Age limit 18-70)
- HCV PCR confirmed active infection, genotype 1 or 3.
- If female, must have negative urine test results for pregnancy during initial screening period (for trial inclusion) and be advised of limited safety data in pregnancy.
- Current illicit drug use established through participant history.
- Able to provide informed consent, agreeing to trial and clinical monitoring criteria

#### **4.3 EXCLUSION CRITERIA**

- Aggressive or violent behaviour.
- Unwilling to consent to GP being informed of their participation in the trial
- Platelet count  $< 75 \times 10^9 /l$
- Alanine transaminase  $> 350U/l$
- Inability to provide informed consent.
- Clinical history or abnormal values for albumin  $< 30 \text{ g/l}$ , Bilirubin  $> 35 \text{ umol/l}$  or PT  $> 1.5$  consistent with decompensated liver failure Childs-Pugh B or C
- Clinical history of primary hepatocellular carcinoma
- Pregnancy or breast feeding.
- Participation in a drug trial within the previous 30 days
- Hepatitis B surface antigen positive
- HIV infection.
- Hypersensitivity to elbasvir and grazoprevir
- Hypersensitivity to sofosbuvir (genotype 3 infected-participants only)
- Currently being treated with an inhibitor of organic anion transporting polypeptide 1B, e.g. rifampicin, atazanavir, daruavir, lopinavir, saquinavir, tipranavir, cobicistat or ciclosporin.
- Currently being treated with inducers of cytochrome P450 3A or P-glycoprotein, such as efavirenz, phenytoin, carbamazepine, bosentan, etravirine, modafinil or St John's Wort (*Hypericum perforatum*)
- Currently being treated with amiodarone (Participants infected with genotype 3 HCV only)

## **5 PARTICIPANT SELECTION AND ENROLMENT**

### **5.1 IDENTIFYING PARTICIPANTS**

- Individuals will be identified via the current DBS testing pathway in Needle Exchange centres sited in health care hubs by specialist nurse or other trained member of staff.
- In addition, known HCV positive participants with reactive dry blood spot test attending needle exchange with status having previously been established elsewhere will be approached in Needle Exchange centres or other suitable venues by specialist nurse or other trained member of staff.
- Potential participants (above) will be given a participant information sheet (PIS) and any questions they have about the trial will be answered by the trial team.

### **5.2 CONSENTING PARTICIPANTS**

Potential participants will be approached by research nurses but they may delegate to other individuals who are trained in dried blood spot testing and are part of the managed care network and have right of referral to treatment services. Any such delegation will be recorded on the trial Delegation Log and be authorised by the CI. Potential participants will be provided with information on the trial verbally and via the PIS and be given at least 24 hours to consider participation in line with prevailing TASC SOP. At their return visit for screening they will be interviewed by the trial research nurse and asked to sign an informed consent form once they are satisfied that they have had adequate explanation from the member of staff explaining the trial to them.

Where a participant requests to speak with a physician from the trial team the consent process will not be completed until the participant had spoken to the physician and had all their questions answered to their satisfaction.

Once a participant has consented to take part a GP letter will be sent to their GP to inform them that their patient is in a clinical trial. If the individual is not registered with a GP they will be encouraged to do so. In the meantime, any acute medical problems will be handled by the hepatitis C clinical team.

### **5.3 SCREENING FOR ELIGIBILITY**

Following informed consent, blood will be taken from the participants to assess their liver function and to confirm that they have active infection with HCV genotype 1 or 3 and not with HIV or hepatitis B. Active illicit drug use will be confirmed by participant. Urine sample will be taken from female potential participants and a pregnancy test carried out to confirm that they are not pregnant. Any prescribed medication will be checked for drug-drug interactions with trial medication.

## 5.4 INELIGIBLE AND NON-RECRUITED PARTICIPANTS

Ineligible or non-recruited participants will be thanked for their interest in the trial and be given a clear explanation as to why they are ineligible. If a clinically significant abnormality is detected relevant clinical management will be instigated and the participants GP informed if the patient consents.

## 5.5 RANDOMISATION

### 5.5.1 Randomisation

After successful screening for eligibility and safety, participants will be randomised to either DOT, fortnightly pick up or fortnightly pick up with psychological intervention.

PWID who are eligible for this trial have unpredictable and chaotic lives. It is therefore possible that an individual will consent to take part, provide baseline information and have blood taken for safety and eligibility checking. If eligible they may be randomised. They may then not be seen at the needle exchange for a number of weeks or even months. It is standard clinical practice that pretreatment bloods are valid for a period of 6 months and therefore we will consider baseline bloods taken for the study to be valid for 6 months unless there is a clinical indication to repeat within that period. Any clinical decision on whether bloods need to be repeated within 6 months will be made by the CI. If a consented participant reappears after a period longer than 6 months has elapsed, a documented verbal check will be made to confirm that the individual continues to consent to taking part in the study. The bloods will be re-taken and eligibility will be based on the results of these new blood tests. The blood tests taken closest to the date of treatment initiation will be considered as the baseline data. The viral genotype will not be retested as NHS lab policy is to redo this test only after 5 years have elapsed. After 6 months the baseline CRF will also be repeated to provide up-to-date pretreatment information. In this case, the information originally collected in the baseline CRF will be filed but will not be entered into the electronic data management system (Openclinica) and will not form part of the analysed dataset. To ensure that the correct, most up-to-date baseline data is entered into Openclinica, baseline data will be entered once each participant has started their treatment.

As this is an un-blinded trial, the nurse, or delegated member of staff, and participant will be aware of which arm they are allocated to. Randomisation to each of the three trial groups will be stratified by genotype so that the proportion of genotype 1 vs genotype 3 infected participants will be the same in each group. The Tayside Clinical Trials Unit (TCTU) GCP-compliant online randomisation system, TRuST, will be used by the specialist nurse or delegated, trained member of staff to perform the randomisation.

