### **5.5.3 Withdrawal procedures**

Participants will be informed that they have the right to withdraw from the trial at any time without giving reasons and without prejudicing further treatment. The right to refuse to participate without reasons will be respected. After the participant has entered the trial the clinician remains free to give alternative treatment to that specified in the protocol at any stage if he/she feels that it is in the participant's best interest but, reasons for doing so will be recorded. In these cases the participants remain within the trial for the purposes of follow-up and data analysis.

Although a participant is not obliged to give reason(s) for withdrawing prematurely, if the participant appears lost to follow up, the CI will make a **reasonable** effort to ascertain the reason(s), while fully respecting the individual's rights, and will demonstrate that everything possible was done in an attempt to find any participant lost to follow-up. Those lost to follow-up or withdrawn will be identified and a descriptive analysis of them provided, including the reasons for their loss and its relationship to treatment and outcome.

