### **6.2 DOSING REGIME**

Following randomisation, participants in the DOT group will be issued with their first dose of medication. Those with genotype 1 infection will be given one Zepatier tablet whilst those with genotype 3 will get one Zepatier tablet and one Sovaldi tablet. Participants in each of the fortnightly dosing regimens will be given two week's supply of medication. No per body weight dose adjustment is required and participants with genotype 1 will be treated for 12 weeks, those with genotype 3 for 8 weeks. 12 weeks following the end of treatment blood will be taken from

participants in order to establish whether they have achieved SVR12. Participants will be asked to consent to being followed up annually for five years to enable us to establish reinfection rates. Participants will be asked to use adequate contraception (see section 11.1).

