### 9.2.3 Statistical analysis

Outcomes Data Analysis plan: Analysis of the trial will follow the principles outlined in the ICH E9 'Statistical Principles for Clinical Trials' and carried out by the UKCRC registered Tayside

Clinical Trials Unit (TCTU). Prior to data lock an agreed Statistical Analysis Plan (SAP) will be finalised covering the pre-specified statistical analysis.

The primary outcome of SVR will be assessed as a binary outcome for subjects and so will utilise logistic regression modelling. The numerator will be the number of subjects achieving SVR and the denominator will be total number of patients randomised to each arm. Additionally results will be expressed as a proportion of the estimated HCV infected subjects in needle exchange. The estimated number of infected patients will be based on national survey data and the empirical rate discovered in the trial (allowing for patients who refuse testing). A test of interaction between contingency and pathway will be carried out and if not significant contingency will be assessed independently. If significant then the effect of contingency will be assessed by each pathway separately. As all patients will have either achieved SVR or not and we will assume that drop-outs / lost to follow-up are failures, there will be no missing data in the primary outcome. Extra- binomial variability or over-dispersion will be examined in the logistic model and if present alternative modelling such as negative binomial models will be considered. This will also be adjusted by therapy and genotype; the two factors are interdependent determining length of therapy.

Secondary binary outcomes will be analysed in the same procedure, initially as intention to treat with all eligible patients as the denominator and then to explore the steps in the pathway by per protocol analysis in particular to analyse on treatment success:

- a) Proportion of HCV tested.
- b) Proportion who start HCV treatment within the duration of the study of those identified with HCV.

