- c) Adherence: to compare the longitudinal evolution of adherence to the prescribed regimen between the conventional pathway and the pharmacy led pathway. For each patient, daily adherence will be defined using a binary variable  $Z_t$  indicating whether yes ( $=1$ ) or no ( $=0$ ) the subject has taken their medication on day  $t$ . This longitudinal binary variable will be directly generated from the patient electronically compiled dosing history. Comparison of binary time series is realized using a logistic regression where dependence among observations from a given patient over time is taken into account. The effect of pathway and contingency management on overall adherence will be tested using the above-described model by testing if either the group coefficient or the interaction between the group and time are significantly different from zero.
- d) Proportion who complete the course of those initiating treatment.

Multiple logistic regression modelling will explore the patient and pathway characteristics that are associated with the secondary outcomes and primary outcome. Patient outcomes considered will be age, gender, deprivation, employment, comorbidity, and the psycho-social variables assessed.

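### Section 5.5.1 makes treatment start the trigger for entering baseline data, so randomised participants who never start would have none in the trial database

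*Protocol*

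**What the plan says.** Section 5.5.1 describes a population that is hard to keep in contact with. After consent, baseline information, bloods and possibly randomisation, it warns: "They may then not be seen at the needle exchange for a number of weeks or even months". If more than 6 months pass, bloods and the baseline CRF are repeated, and "the information originally collected in the baseline CRF will be filed but will not be entered into the electronic data management system". To make sure that the newest version is the one entered, "baseline data will be entered once each participant has started their treatment". The section gives no rule for someone who is randomised and never starts.

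Section 9.2.3 says of the primary outcome that "the denominator will be total number of patients randomised to each arm" and that "we will assume that drop-outs / lost to follow-up are failures". It adjusts the primary model by therapy and genotype. It then adds: "Multiple logistic regression modelling will explore the patient and pathway characteristics that are associated with the secondary outcomes and primary outcome". The covariates named are age, gender, deprivation, employment, comorbidity and psycho-social variables.

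The Summary describes a different analysis set: modified intention to treat, limited to participants who took at least one dose.

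Section 5.5.3 promises that "Those lost to follow-up or withdrawn will be identified and a descriptive analysis of them provided", covering reasons for loss and how loss relates to treatment and outcome.

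**The concern.** Whether a participant's baseline data reach the database depends on something that happens after randomisation. The trial is unblinded, so starting treatment may be influenced by the allocated arm. Section 1.2 raises the possibility that directly observed therapy (DOT) could put people off taking up treatment.

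Under section 9.2.3 every never-starter is in the denominator and is a failure. Without baseline data these people would be absent from the baseline table and from the exploratory models of SVR, and all of those missing would be failures. The baseline table would describe starters only. The models meant to show who fails would lose one whole kind of failure, and at a high SVR rate failures carry most of the information.

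**Working it through.** **Which analyses need the baseline CRF**

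| Planned output | Data needed | Available for never-starters? |
|---|---|---|
| SVR rate by arm (9.2.3) | Arm, outcome (scored as failure) | Yes |
| Primary logistic model (9.2.3) | Arm, genotype, outcome | Yes: arm and the stratification factor are known at randomisation |
| Exploratory models of SVR (9.2.3) | Age, gender, deprivation, employment, comorbidity, psycho-social variables | Not from the database |
| Baseline table | Baseline CRF | Not from the database |
| Description of those lost (5.5.3) | Reasons, arm, outcome | Yes; baseline characteristics, if wanted, not from the database |

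**The protocol's sample size (section 9.1)**

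Inputs: 95% SVR in both compared arms, margin 14 points, one-sided 5%, power 90%.

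n = (1.645 + 1.282)² × (2 × 0.95 × 0.05) / 0.14² = 8.56 × 0.095 / 0.0196 = 41.5, so 42 per group. This matches the stated figure. Recruiting 45 per group allows 3/45 = 6.7% drop-out, or 135 − 126 = 9 people.

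**Share of failures without baseline data**

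The protocol gives no never-starter rate. Assume N never-starters, 95% SVR among starters in all arms (section 9.1 states 95% for the DOT arm), and no other drop-outs.

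All failures = N + 0.05 × (135 − N)

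- N = 3: 3 + 6.6 = 9.6; share 3/9.6 = 31% (roughly 3 in 10).
- N = 9, the whole drop-out allowance: 9 + 6.3 = 15.3; share 9/15.3 = 59%.

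**A wider range, as a proportion s of those randomised**

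| s | Never-starters (135 × s) | Per arm with baseline data (45 × (1 − s)) | SVR, all randomised (0.95 × (1 − s)) | SVR, starters only |
|---|---|---|---|---|
| 5% | 6.75 | 42.75 | 90.3% | 95% |
| 10% | 13.5 | 40.5 | 85.5% | 95% |
| 20% | 27 | 36 | 76.0% | 95% |

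The number per arm with baseline data falls below 42 once s exceeds 6.7%. This only gives a sense of scale, since the exploratory models were not powered on 42.

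**If never-starting differs by arm**

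Assume 15% in one arm and 5% in another, with 95% SVR among starters in both. The all-randomised difference is 0.95 × (0.95 − 0.85) = 9.5 points, against a margin of 14. The starters-only difference is 0. The primary analysis would show the 9.5 points, but models confined to starters could not explain them.

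**The case against.** The strongest reply is that the entry rule fits the Summary. If only participants with at least one dose are analysed, never-starters are outside the set and need no covariates. That is a fair reading of the Summary, but section 9.2.3 says otherwise. Even under the one-dose set, baseline data on the people excluded are needed to judge whether their exclusion unbalanced the arms.

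Second, the rule is version control. It expressly keeps out of the database only those baseline forms superseded by a repeat after 6 months. A reader might infer that never-starters have no baseline record at all. The documents do not support that: the form is completed before randomisation and stays on file, and nothing forbids entering it before data lock. Still, the protocol's only trigger for entry never occurs for these people.

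Third, few may be affected. Section 6.2 says "Following randomisation, participants in the DOT group will be issued with their first dose of medication", and both matrices in Appendix 2 put drug administration on Day 0 of the randomisation visit. This stands, and the number could be close to zero. Section 5.5.1 nevertheless plans for the gap.

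Fourth, section 9.1 leaves missing data to the SAP, which is not at hand, so deletion of incomplete cases is an assumption here. This also stands. But a SAP method would have only arm, genotype and outcome to work from for these participants unless their forms are entered.

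**Conclusion.** The point holds in a limited form. As written, section 5.5.1 leaves randomised never-starters without baseline data in the trial database, while section 9.2.3 counts them as failures. The baseline table and the exploratory covariate models of SVR are affected, as is any baseline description of those lost. The size cannot be fixed from the protocol. Roughly 30% to 59% of failures rests on 3 to 9 never-starters, 95% SVR among starters in every arm, no later drop-outs, and models that omit people without covariates. The upper end is a worst case because it spends the entire drop-out allowance on never-starters.

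Three stronger conclusions that a reader might draw are not supported:

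- That the primary comparison is compromised. Its adjustment factors are known at randomisation, so it can be fitted on everyone randomised.
- That the analysis promised in section 5.5.3 cannot be done. That section names reasons, treatment and outcome, and does not name baseline characteristics.
- That the protocol expects never-starting to differ by arm. Section 1.2 says only that DOT may discourage uptake.

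This is a worthwhile, inexpensive correction to a stated rule and does not threaten the main result.

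**What to change.** In section 5.5.1, replace the treatment-start trigger with a requirement to enter baseline data for every randomised participant. If baseline is repeated after 6 months, enter the repeat as a separate dated record and use the one closest to treatment start. For those who never start, use the last baseline before randomisation. This keeps the section's aim of analysing the most recent pre-treatment data.

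Reconcile the Summary's one-dose set with the all-randomised denominator in section 9.2.3, so that it is clear whether never-starters count in the primary analysis.

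The cost is a short text change, a repeatable baseline form in OpenClinica and a few extra records. There are no new assessments and the sample size does not change.
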